- Describe the causes of non-performance of the confirmatory test and identification of predictors of non-performance or postponement of the diagnostic test within a maximum period of 90 days from the initial recommendation.

Study design

Overview

Study, prospective, open, randomized, controlled.

Justification of the main elements of the protocol

The FINDRISC screening questionnaire has been previously studied and validated, can be applied quickly, economically and its low complexity makes them widely available (5,10). Similarly, previous studies have shown that periodontal disease is related to the appearance of alterations in the glycemic profile so that up to 30% of adults over 30 years of age who attend general dentistry consultations are identified as a population at risk (3).

Despite the drawbacks to its mass application, OGTT remains included within the current CPGs and continues to be a reference test for the diagnosis of patients with DM2 (3).

Measurement of A1c may be more convenient than OGTT, particularly if performed at the point of care (POC-A1c). Additionally, the characteristics for its implementation and its technical profile are clearly established. However, its impact on the screening algorithm under real conditions of use is unknown and its profile for inclusion within a mass screening system has not yet been established.

Setting the primary endpoint

While it is possible to perform screening using any of the validated questionnaires, in real conditions of their implementation a second visit of the patient is required to perform a confirmatory test (GTT) and the loss to follow-up is required a major challenge for health systems. It is proposed that the implementation of POC-A1c can contribute to improving the follow-up rate in the context of population screening and facilitate the successful implementation of large-scale screening campaigns.

Therefore, the primary outcome is the probability of going to OGTT according to the strategy implemented.

Choice of comparator

Currently, the screening guidelines contemplate the completion of the FINDRISC questionnaire followed by a confirmatory test carried out in the centralized laboratory. Because of this, the recommended practice is established as a comparator.

Type of design

Prospective, open label, randomized, controlled study in adults with no known diagnosis of diabetes.

Study procedures

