- **Bias in outcome measurement:** the outcome of the OGTT sampling is sufficiently robust not to be affected by the research team, the participant itself or external factors.
- **Bias in the selection of the reported result:** at this point it is mentioned how the creation of surrogate outcomes not proposed in the protocol will be avoided and how consistency will be maintained in terms of the applicability of statistical terms, that is, only what is proposed in the data analysis will be carried out.

Statistical analysis plan

Description of statistical methods

For the primary objectives, the proportions of patients who attended the performance of the GTT in each of the groups will be obtained and the statistical significance test will be applied for superiority in the follow-up ratio of the intervention group (A) over the control group (B). Additionally, descriptive statistics will be obtained regarding the dynamics of application of the confirmatory test (i.e., latency time).

The variables will be checked for normality using the Kolmogorov-Smirnoff test. For quantitative variables, data shall be expressed as mean and standard deviation, or median and interquartile range 25%-75%, as the case may be.

For qualitative variables, proportions (%) will be determined. The continuous data between both groups will be analyzed with the T test if the distribution of the variables is normal or with the Mann-Whitney test if they are not. The analysis of the categorical data between two groups will be carried out with the chi-Square or Fisher test as appropriate.

An analysis will be carried out on the conditional probability of reaching a OGTT test: $P(\text{perform OGTT} | \text{FINDRISC} \geq 12)$

$P(\text{perform OGTT} | \text{POC-A1c} \geq 5.7\% \text{ and FINDRISC} \geq 12)$

An analysis will be performed to identify risk factors for not performing the PGT, the dependent variable will be dichotomous. The main independent variable will be dichotomous corresponding to the control and intervention group. The control variables will be: age,

	
Effectiveness comparison of the hemoglobin measurement glycosylated at the point of care (POC-A1c), vs the standard current based on tolerance test oral to glucose, for the detection early of Diabetes Mellitus guy 2 (DM2) in Colombia. EDDIT-1 STUDY
	
Version: 3.0 Date: February 15, 2022

---	--	---

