gender, type of affiliation, FINDRISC score and POC-A1c value (for those in which it is available) and others that are considered possible variables of confusion.

In order to analyze these associated factors, it is proposed to carry out a generalized linear model of binomial type or poisson type with robust errors, in order to evaluate the influence of the factoris sociodemographic and with relevance / biological and contextual plausibility in the aforementioned outcome (non-realization of OGTT). The partnership measures will be presented through RR with their corresponding 95% confidence interval. A bivariate and multivariate analysis will be carried out to identify possible confusion or interaction for which the probability of performing the OGTT should be adjusted. Under the methodology proposed by Furnival-Wilson (1974) a reduced model will be estimated, using the logarithmic probabilities of the candidate models in order to establish the most parsimonious model. The goodness of fit of the models and the assumptions underlying the selected methodology will be evaluated. The statistical package where the analyses will be carried out is Stata 16MP.

Sample size

The study is designed to detect a 10% difference in going to the laboratory for OGPT between the intervention group (60%) and the control group (50%) considering a power of 80% and a confidence interval range of 95%.

Considering that some people with positive FINDRISC (i.e., greater than or equal to 12) will have a normal APOC-A1c, the number of participants in the intervention group (i.e., group A) will be increased by 30% to ensure sufficient subjects available for analysis with completely positive classification. This percentage corresponds to patients without glycemic alterations or DM2 identified in the FINDRISC validation study (9).

According to this and considering that the primary endpoint is a categorical variable, an initial sample of 784 randomized subjects (392 in each arm) was calculated, after the adjustments the sample is of 902 subjects distributed asymmetrically (510 in group A or intervention and 392 in group B or control).

It is expected that the proportion of patients with FINDRISC greater than or equal to 12 will be 30% of the patients to whom the questionnaire is applied, according to this the expected total of Sieved patients is 3005. However, the total number of patients screened can be extended to complete the goal of randomized patients.

Level of significance

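### Predictors of not doing the OGTT come from a subset search with uncorrected 95% CIs, which lose nominal coverage, and the chosen model depends on a binomial-or-Poisson choice left open

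*Combined protocol and SAP*

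**What the plan says.** The last secondary objective includes "identification of predictors of non-performance or postponement of the diagnostic test within a maximum period of 90 days". The analysis is set out under Description of statistical methods:

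- Outcome: "An analysis will be performed to identify risk factors for not performing the PGT, the dependent variable will be dichotomous".
- Exposure: "The main independent variable will be dichotomous corresponding to the control and intervention group".
- Covariates: age, gender, type of affiliation, FINDRISC score and POC-A1c where available, "and others that are considered possible variables of confusion". The list is therefore open.
- Family: "generalized linear model of binomial type or poisson type with robust errors". No rule is given for choosing between the two.
- Reporting: "The partnership measures will be presented through RR with their corresponding 95% confidence interval".
- Selection: "Under the methodology proposed by Furnival-Wilson (1974) a reduced model will be estimated, using the logarithmic probabilities of the candidate models". The stated aim is parsimony.

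I read the logarithmic probabilities as log-likelihoods, and the Furnival-Wilson method as an all-subsets (leaps-and-bounds) search. The plan names no penalty such as AIC or BIC. It describes no bootstrap, shrinkage, validation or post-selection interval, and does not say whether arm is kept in every candidate model. It does say that goodness of fit and model assumptions will be evaluated. The section Selection of subjects to be included in the analyses limits the analysis to people with complete data.

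**The concern.** There are two separate problems.

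1. **Intervals after selection.** A covariate survives the search because its estimate in this sample is far enough from zero. An ordinary 95% CI treats the model as fixed in advance and ignores that. Among the predictors that are reported, coverage is no longer 95%, and weak effects look larger than they are.

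2. **Selection on a Poisson log-likelihood.** A Poisson model with robust errors gives sound risk ratios and intervals for a yes/no outcome. The robust step corrects the variance only; the log-likelihood that ranks the models is still that of a count. A penalised comparison on that scale is miscalibrated.

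In addition, raw log-likelihood never falls when a term is added to a nested model, so a search for the most parsimonious model needs a penalty. Without one the rule cannot be reproduced. The Bias Control section undertakes to do only what the analysis plan proposes, and that undertaking cannot be checked against an incomplete rule.

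At stake is which factors the trial reports as predictors of non-attendance, and how firmly.

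**Working it through.** **Inputs from Sample size.** Attendance 60% and 50%, so non-attendance 40% and 50%; 510 in group A, 392 in group B; 80% power; 95% confidence.

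**The plan's own figure.** Two proportions, two-sided 0.05, pooled variance:

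n = [1.96 × √(2 × 0.55 × 0.45) + 0.842 × √(0.25 + 0.24)]² / 0.10² ≈ 388 per arm, against 392 stated (close). Then 392 × 1.3 = 509.6, so 510, and 510 + 392 = 902. The sample size is not in dispute. The predictor analysis has no figure of its own.

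**Expected events.** 0.40 × 510 + 0.50 × 392 = 204 + 196 = 400. μ = 400/902 = 0.443 and 1 − μ = 0.557.

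**Cut-offs implied by a penalty k per parameter** (AIC: k = 2; BIC: k = ln 902 = 6.80; both are assumptions).

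- Binomial likelihood: a term is kept when |z| > √k.
- Poisson likelihood on a binary outcome: the likelihood-ratio statistic is about (1 − μ)z², with z the robust statistic, so a term is kept when |z| > √(k/(1 − μ)).

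| Penalty, family | Cut-off | Null term kept (p) | CI covers 1, given kept |
|---|---|---|---|
| AIC, binomial | 1.41 | 15.7% | 68% |
| AIC, Poisson | 1.90 | 5.8% | 14% |
| BIC, binomial | 2.61 | 0.9% | 0% |
| BIC, Poisson | 3.50 | 0.05% | 0% |

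The last column is max(0, (p − 0.05)/p); for example (0.157 − 0.05)/0.157 = 0.68. For μ from 0.40 to 0.50 the Poisson AIC cut-off runs from 1.83 to 2.00 and the last column from 26% to 0%.

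**Unconditional rate under AIC** (null kept and CI excludes 1): 15.7% × 31.8% = 5.0% for binomial; 5.8% × 86.2% = 5.0% for Poisson. This equals the rate with no selection.

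**A true predictor with 80% power** (mean z = 2.8). Kept under AIC: 92% binomial, 82% Poisson. Kept under BIC: 58% and 24%.

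**Simulation of the search.** Assumed: 510 + 392 participants, arm forced in, six uncorrelated covariates (two with RR 1.08 per SD, four null); 800 Poisson and 300 log-binomial runs.

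- Coverage over all retained covariates: log-binomial about 89% (AIC) and 88% (BIC); Poisson about 82% and 68%.
- Retained null terms, log-binomial AIC: 67.5%, against 68% in closed form.
- Retained weak true predictors under AIC: 96–98%. Their log-RRs were inflated 1.18–1.33 times (AIC) and 1.5–1.9 times (BIC).
- Ratio of standard errors, selected to full model: 1.00.
- Arm RR coverage: 0.936–0.940 after selection, 0.929–0.940 in the full model.
- Full model with no selection: 0.946–0.955 for covariates.

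**Does the family matter?** Two further sets of 120 runs (covariate correlation 0 and 0.3) compared the families under AIC. They ended on the same model in 46% and 39% of runs, and on the same best subset of a given size in 84% and 83%. Dividing the Poisson log-likelihood by 1 − μ brought the share of runs with at least one null term kept back to the log-binomial level: 52% against 48%, and about 62% against 63%. Uncorrected Poisson gave 21% and 32%. The disagreement over the final model therefore comes largely from the penalty's scale, less from the ranking of models of equal size.

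**The case against.** Several stronger readings are tempting, and the documents do not support them.

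- *A reader might infer that selection creates more false predictors.* It does not. The chance that a null predictor is kept with a CI excluding 1 is 5.0% under AIC for either family. Six null predictors give at least one such result in 1 − 0.95⁶ = 26.5% of trials with no selection at all, and the full model would not lower that.
- *That the intervals are too narrow.* The standard errors were unchanged in simulation. The fault is off-centre estimates.
- *That the Poisson option is unusable.* Its risk ratios and robust intervals are sound. Its selection is conservative, and it mostly agrees with the binomial ranking at equal model size.
- *That many true predictors will be lost.* That needs BIC. Under AIC the loss is small, and the plan names neither.
- *That arm will be dropped, or that only the reduced model will be reported.* The plan says neither. Arm is called the main independent variable, and the sentence on risk ratios comes before the one on reduction.

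It is also fair to say that this is one part of the last-listed secondary objective and that the plan sets a significance level for the primary objective only. All of this stands. It leaves the core in place: no correction is described, checks of fit and assumptions do not supply one, and the criterion and the family are open.

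**Conclusion.** The point holds in a limited form. Ordinary 95% CIs for predictors retained by the search do not have 95% coverage, and under the Poisson option the search uses a miscalibrated log-likelihood, so the selected model depends on an unspecified choice.

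The closed-form figures rest on an assumed penalty, n = 902 and the plan's design attendance rates. The simulated figures also depend on assumed covariates and effect sizes. That the CIs will be ordinary ones is inferred from the absence of any other method. Undercoverage falls mainly on retained null predictors; under BIC with Poisson, weak true predictors also suffer (about 68%).

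The primary comparison of proportions and the sample size are untouched, and the arm RR was not materially affected in simulation. The point should be settled before analysis, but it does not threaten the trial's main result.

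**What to change.** Amend Description of statistical methods as follows.

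1. Fix one family in advance, for example Poisson with robust errors.
2. Report risk ratios and 95% CIs from one full pre-specified model, with no subset search: arm forced in, plus age, gender, affiliation, FINDRISC score and the sociodemographic variables in Annex 4. Close the open-ended covariate list before the data are analysed.
3. Examine POC-A1c in a separate group A model. It is measured only in that group, so a complete-case model containing it would exclude group B and leave no arm contrast.
4. If a reduced model is also shown, name the criterion, select on the binomial or a dispersion-corrected likelihood, bootstrap the whole selection to obtain intervals, and label the result exploratory.

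**Feasibility.** Coefficients by Annex 4 levels: marital status 5, schooling 5, employment 1, stratum 1 (as a score) to 5 (as categories), affiliation 2, and one each for arm, age, gender and FINDRISC. The total is 18 to 22. With 400 expected events that is 400/22 ≈ 18 to 400/18 ≈ 22 per coefficient before complete-case loss, so reduction is not needed for stability.

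**Cost.** SAP wording only: no new data or participants. The model table is longer and some parsimony is lost. Intervals were no wider in the simulation with uncorrelated covariates; correlated covariates could widen them somewhat.

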
Procedures
	
The doctor explains what the study consists of and obtains informed consent. If the patient accepts, the FINDRISC will be verified, the inclusion and exclusion criteria are verified and the relevant data from their medical history will be recorded.
 
Subsequently, the subjects will be included in the study and randomized into two groups. In the participants of group A (intervention) they will be offered information on healthy lifestyles according to their result in the FINDRISC questionnaire and then a measurement of POC-A1c. In the participants of group B (control) they will be offered the same information on healthy lifestyles according to their FINDRISC result.
 
In addition, all randomized participants will be invited to perform a GPOT in the allied work of CAIMED or in the laboratory of their choice with the necessary preparation recommendations for the realization of the same. For this purpose, they will be given an order that includes the date of screening, a tracking number and time window in which they must go (i.e., 30 days and with a second attempt-maximum window at 90 days).
 
After 30 days from the delivery of the order for the PGTO, a call will be made to the randomized subjects to check if the exam was taken and its result requested in case it has done so, if the examination, you must send it to the center. Otherwise, the causes of not having made the previously recommended GTT will be investigated, and a new call will be made after 90 days. In patients who, if they attended the performance of the OGTT and obtained a presumptive result of diabetes (defined as an impaired oral glucose tolerance test and/or impaired POCA1C test according to the ADA guidelines), a closing call will be made 30 days after the test was done to confirm if they started to control their disease. For this, it will be instructed to attend consultation by general medicine according to what is contemplated by its entity administering benefit plans, ending the follow-up.
	

Analysis plan
	
For the primary objectives, the proportion of patients who attended the performance of the PGTT in each of the groups will be obtained and the statistical significance test for superiority in the follow-up ratio of the intervention group (A) over the control group (B) will be applied. Additionally, descriptive statistics will be obtained regarding the dynamics of application of the confirmatory test (i.e., latency time).
	

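### Group A is enlarged to 510 by multiplying 392 by 1.30, which does not offset a 30% share with normal POC-A1c: about 357 A1c-positives are expected, not 392

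*Combined protocol and SAP*

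**What the plan says.** The Sample size section plans for OGTT attendance of 60% in the intervention group against 50% in the control group, with 80% power and 95% confidence, and arrives at 392 per arm. It then adjusts group A only. The reason given is that "some people with positive FINDRISC (i.e., greater than or equal to 12) will have a normal APOC-A1c", so group A is "increased by 30% to ensure sufficient subjects available for analysis with completely positive classification". The source of the figure is given as follows: "This percentage corresponds to patients without glycemic alterations or DM2 identified in the FINDRISC validation study". The outcome is that "after the adjustments the sample is of 902 subjects distributed asymmetrically (510 in group A or intervention and 392 in group B or control").

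Biochemical measurements counts a POC-A1c of 5.7% or more as impaired, so normal means below 5.7%.

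Two analyses could draw on these numbers. Description of statistical methods plans one on the A1c-positive subset: "An analysis will be carried out on the conditional probability of reaching a OGTT test", given POC-A1c of at least 5.7% and FINDRISC of at least 12. The primary analysis uses whole randomised groups. The Analysis plan in the Protocol Synopsis says that the "statistical significance test for superiority in the follow-up ratio of the intervention group (A) over the control group (B) will be applied", and Description of statistical methods repeats this.

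**The concern.** The 30% is described as the share of people who will not be A1c-positive. It is therefore a fraction lost from the enlarged group, and the usual way to end up with a required number is to divide by one minus that fraction. The plan adds 30% to the starting number instead, which always falls short of the offset.

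This adjustment is the only reason given for unequal arms and for 510 − 392 = 118 additional participants in group A. A reader of the section would conclude that the A1c-positive set is kept at its planned size. At the plan's own percentage it is not. What is at stake is the precision of one planned estimate and the accuracy of the sample-size statement. The section also leaves two things open: whether the 60% was meant for all of group A or only for its A1c-positive members, and what power the final 510 against 392 provides.

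**Working it through.** **Inputs.** From Sample size: 60% vs 50%, 80% power, 392 per arm, 30%, 510, 902, 3005 screened, 30% of those screened at FINDRISC 12 or more. From Level of significance: 0.05. The plan does not state sidedness; two-sided is used because it reproduces 392, whereas a one-sided test gives 305.

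**1. Reproduce the plan's figures.**
- Base size, with variance taken at p = 0.5: (1.96 + 0.84)² × 2 × 0.25 / 0.10² = 392 per arm.
- Inflation: 392 × 1.30 = 509.6, rounded to 510.
- Total: 510 + 392 = 902.
- Screening: (509.6 + 392) / 0.30 = 3005.3, matching the plan's 3005. This confirms the multiplier of 1.30.

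**2. What the multiplier offsets.**
- Loss fully offset by × 1.30: 1 − 1/1.30 = 0.231, or 23.1%.
- Size needed to offset 30%: 392 / 0.70 = 560.

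**3. Expected A1c-positives among 510.**
- At 30% normal: 510 × 0.70 = 357. Shortfall against 392: 35, and 35/392 = 8.9%.
- At other normal shares (assumed range, not in the documents):

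| Normal share | Expected A1c-positives |
|---|---|
| 20% | 408 |
| 25% | 383 |
| 30% | 357 |
| 35% | 332 |
| 40% | 306 |

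**4. Effect on the conditional probability.** The 95% half-width is 1.96 × √(p(1 − p)/n), with p = 0.60 borrowed from the design as a planning value.
- n = 357: 1.96 × √(0.24/357) = 0.0508, or 5.1 points.
- n = 392: 1.96 × √(0.24/392) = 0.0485, or 4.8 points (0.04850 before rounding down from 4.850).

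**5. Effect on the primary comparison.** Two proportions, two-sided 0.05, pooled variance under the null, 60% in all of A against 50% in all of B:
- 392 vs 392: 80.5%.
- 510 vs 392: pooled proportion (0.60 × 510 + 0.50 × 392)/902 = 0.5565; null standard error 0.03337; alternative standard error 0.03329; power = Φ[(0.10 − 1.96 × 0.03337)/0.03329] = 85.1%.
- The same with equal loss in both arms (assumed rates, not in the documents): 83.2% at 5%, 81.2% at 10%, 79.0% at 15%.

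**The case against.** The strongest reply is that the plan promises an increase of 30% and delivers exactly that. It asks only for enough positives and never says 392, so the shortfall exists only against an inferred target. That is fair, and the conclusion is conditional on it. Still, 392 is the number being inflated and the plan offers no other meaning for enough.

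Second, the 30% comes from a validation study whose details are not in the documents. They do not say whether glycaemic alteration was judged by A1c or by glucose, or whether the share refers to people with FINDRISC of 12 or more. It may not equal the share with POC-A1c below 5.7%. The assumed range above (306 to 408) is wider than the shortfall, and at 20% normal the 510 would exceed 392. This stands as a limit on the size of the shortfall. It does not rescue the step, because the plan itself uses the 30% for this purpose.

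Third, the practical cost is a difference of about 0.2 to 0.3 points in half-width on a secondary estimate with no stated precision target. This stands in full.

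A reader might infer that the trial is underpowered or that 560 must be randomised to group A. The documents do not support either. The primary test compares whole groups, group B stays at 392 and group A only grows, so under the stated rates power rises above the 80.5% of the equal design. A reader might also set 357 A1c-positives against 392 controls and report 78.6% power. The plan specifies no such test, and it would not be a randomised comparison, because group B has no A1c result.

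**Conclusion.** The inflation step does not deliver the purpose given for it. At the plan's 30%, 510 is expected to yield about 357 A1c-positives, 35 (8.9%) below the 392 that was inflated; keeping 392 would take 560. This rests on two assumptions: that 392 is the intended number of positives, and that 30% of group A will have POC-A1c below 5.7%.

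The consequence is minor: slightly less precision for the conditional probability. The primary comparison is not harmed. The figure of about 85% for 510 against 392 assumes that the 60% applies to all of group A, which is the literal reading of the Sample size section, and that outcome data are complete. The second condition matters because Selection of subjects to be included in the analyses keeps only people with complete data, withdrawn subjects are not replaced, and the sample size carries no allowance for loss. With equal loss of 15% (assumed), power would be just under 80%.

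**What to change.** First, the sponsor should confirm whether the assumed 60% attendance applies to all of group A or only to its A1c-positive members. No text on power should be inserted before that answer.

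Then restate in the Sample size section, without enrolling more:
- The 510 in group A are expected to include about 357 with POC-A1c of at least 5.7%, if 30% are below 5.7%. Do not describe 510 as preserving 392.
- If the 60% applies to all of group A: power for 510 against 392 is about 85% with complete outcome data, and lower with loss (for example 83%, 81% and 79% at assumed equal loss of 5%, 10% and 15%).
- If it applies only to A1c-positives: say so, and give power under a stated attendance rate for the A1c-normal members.
- The A1c-positive result stays a conditional probability, as in Description of statistical methods, and is not presented as a randomised comparison with group B.

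The cost is a few sentences, with no added participants, procedures or analyses. Only if the sponsor requires 392 A1c-positives do the consistent figures become 560 in group A and 560 + 392 = 952 in total, 50 more than planned.
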